10 METHODOLOGY

10.1 Screening examination - Visit 1

Screening examination will be performed prior to inclusion and prior to the first intended administration of the IMP to ensure that patients are eligible for the clinical trial.

The following assessments will be performed on Visit 1 (V1):

- demographic (age, sex, ethnic origin) and anthropometric data (body weight, height, BMI)
- medical history (including prior and concomitant medication)
- physical examination vital signs (blood pressure, pulse rate, body temperature (axillar))

Objective examination: skin and visible mucosa, palpation of abdomen and lymph nodes (submandibular, anterior and posterior cervical ones), oropharyngoscopy will be performed to assess the status of the tonsillitis.

Hence, objective symptoms included in the “Local Tonsillitis Manifestation Scale” are assessed using a 4-point rating scale using score “0” absent, “1” mild, “2” moderate, and “3” severe/pronounced. Diagnoses will be refined by using the Mclsaac Scale (see 0)

- clinical laboratory investigation: blood analysis including haematology, haemostatic system, serum chemistry, serology, urinalysis or other laboratory investigations are performed at the discretion of the investigator
- female status (in females with childbearing potential pregnancy test)

Finally, a self-assessment of the patient’s throat pain by him/herself and (or) his/her parent(s) using a visual analogue scale (VAS) is performed.

All data has to be documented by the investigator in the patient’s medical file and recorded in the CRF. Afterwards, inclusion and exclusion criteria are checked by the investigator, documented in the patient’s medical file, and recorded in the CRF.

At the end of Visit 1 the patient will be randomized, sorted to one of the two study groups and IMP will be handed over.

10.2 Status evaluation - Visit 2

The next status evaluation of the disease will be performed on day 3, i.e. ± 1 day after Visit 1 (V1).

A physical examination of vital signs (blood pressure, pulse rate, body temperature (axillar)) will be performed. All physical examinations done at V1 including skin and visible mucosa, palpation of abdomen and lymph nodes, oropharyngoscopy will be repeated to assess the status of the tonsillitis.

Again, objective symptoms included in the “Local Tonsillitis Manifestation Scale” are assessed and diagnoses will be refined by using the Mclsaac Scale (see 0).

Checks for general well-being (AE-checks), checks of restrictions and medication will be performed.

The investigator will estimate indicators for prescription of antibiotics and will decide whether a patient will remain on the study treatment or not. If an antibiotic agent is prescribed, details will be documented and the patient will be instructed about the mode of administration. Intake of

antibiotic drug will be documented in the CRF. Patients with intake of antibiotics will be evaluated separately. At the discretion of the investigator the patient may be advised not to take IMP anymore. If so, this will be documented as well.

Self-assessment of the patient's throat pain by him/herself and (or) his/her parent(s) using a visual analogue scale (VAS) is performed afterwards. Moreover, forms for VAS assessment will be handed over to the patient. The patient will have to assess his/her sore throat every study day until visit 4 on study day 10±1.

10.3 Interim evaluation of treatment efficacy- Visit 3

Visit 3 (V3) will be performed on day 5 ±1 by a telephone call.

Intermediate evaluation of the effectiveness of treatment (day 5-day ±1) via telephone (or visit if necessary); patients self-assessment (VAS; 0-10)

10.4 Treatment efficacy, end of Reference treatment - Visit 4

At visit 4 (V4) on day 10 ±1 the status of the disease will be again evaluated.

A physical examination of vital signs (blood pressure, pulse rate, body temperature (axillar)) will be performed. All physical examinations done at V1 including skin and visible mucosa, palpation of abdomen and lymph nodes, oropharyngoscopy will be repeated to assess the status of the tonsillitis.

Again, objective symptoms included in the "Local Tonsillitis Manifestation Scale".

Checks for general well-being (AE-checks), checks of restrictions and medication will be performed.

Self-assessment of the patient's throat pain by him/herself and (or) his/her parent(s) using a visual analogue scale (VAS; 0-10 points) is performed. Forms of VAS assessment will be collected from the patient.

10.5 Treatment efficacy, end of treatment - Visit 5

Visit 5 (V5) will be performed on day 28 by a telephone call (for both the groups).

Checks for general well-being (AE-checks), checks of restrictions and medication will be performed.

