5 TRIAL SYNOPSIS

Trial code	ATi-2
Title of Trial	A Protocol of a Multicenter, Randomized, Open-Label, Comparative Study of Therapeutic Efficacy, Safety and Tolerability of Imupret application in the therapeutic concept of delayed prescription of antibiotics in children, aged 6-12 with severe acute tonsillitis.
Working title	Imupret in tonsillitis
Trial Design	open-label, exploratory, comparative, multicentre, randomized, prospective, parallel-group study.
Clinical phase	IV
Inclusion diagnosis	Acute tonsillitis
Trial objectives	
Assessment of the influence of Imupret (drops) prescriptions in the therapeutic concept of delayed prescription of antibiotics to:
 
 • need for antibiotics • regression of the tonsillitis symptoms • duration of antipyretics administration
Number of patients	approximately N=200 (1:1 ratio active treatment: reference)
Specialization of investigator	Head of Department of Otorhinolaryngology Head & Neck Surgery
Time schedule	Planned FPI (First patient in): approximately February 2019 Planned LPO (Last patient out): approximately December 2019
Efficacy endpoints	
The main criterion (main variable):
 
 - decrease in the severity of each symptom (complaint) that is part of the Mclsaac scale of tonsillitis manifestations, up to 1 point or less. This variable is dichotomous, with the categories "treatment effective" and "treatment not effective": - Treatment is effective - reducing the severity of each symptom (complaint) that is part of the Local Tonsillitis Manifestation Scale (0-15), of tonsillitis manifestations, up to 1 point or less in the evaluation stages. Absence of indications for prescribing antibacterial therapy - Treatment is not effective - the condition given for the category "therapy is effective" is not met.
Secondary end-points	
Secondary variables:
 
 - a decrease in the severity of the symptoms of the underlying disease, at the 2- nd, 3 -rd and 4- th visits compared to the 1- st visit. - decrease in the total score (the sum of scores for each symptom) according to the scale of local manifestations of tonsillitis at the 2-nd, 3-rd and 4-th visits in comparison with the 1-st visit. - a decrease in temperature in the armpit at the 2-nd and 3-rd visits compared to the 1-st visit. - a patient's self-assessment of the quality of life (every day). - Duration of NSAID administration. -Therapy compliance

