It should be noted that unjustified antibiotic therapy of acute tonsillitis is only based on the symptom "sore throat" or "exudate (plaque) tonsils" and plays a significant role in the formation of antibiotic resistance. Antibiotic therapy does not affect pain. In order to avoid the

irrational use of antibiotics, one should distinguish the desire of the patient or his parents to get rid of the pain, from the rational assessment of the doctor for all pros and cons about an antibacterial therapy.

To prevent unjustified prescription of antibiotics, a therapeutic concept of delayed administration is proposed. A patient with acute tonsillitis is prescribed treatment with antibacterial agents in a delayed manner (a prescription is written out, the dose and the frequency of administration is calculated). In the absence of positive effect within 36-48 hours from the beginning of treatment with Imupret the antibacterial therapy with antibiotics is started. The advantage of deferred antibiotic prescription is, that a higher number of patients and doctors, awaiting antibiotic therapy, may be more agreeable with this way of treatment than with a complete rejection of the antibiotics prescription. This is why delayed use of antibiotics is an important treatment strategy to reduce the number of unreasonable prescription of antibacterial agents.

Considering this fact, it becomes necessary to use drugs with a complex effect on the main processes of pathogenesis and have an evidence-based efficacy base for acute tonsillitis. At the present moment, there is an insignificant evidence base for the application of the phytonoering drug Imupret in acute tonsillitis. The spectrum of its pharmacological properties includes antiviral, antibacterial, antiinflammatory and immunomodulating effects. The combination of these properties makes it possible to influence practically all parts of acute tonsillitis. Additionally a good safety profile allows to consider Imupret as an adequate basic therapy for the treatment of acute tonsillitis, especially in the therapeutic concept of of delayed prescription of antibiotics. The already existing studies were not conducted under GCP conditions. Confirmation of the high effectiveness of Imupret in the treatment of acute tonsillitis would serve as a rationale for optimizing the treatment regimen of this nosology and recommendations for the inclusion of the drug in national guidelines.

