6.3 Description and rationale for conducting the trial

At present, there is minor evidence of using the phytoengineering-based drug product Imupret® in acute tonsillitis, pharyngitis and tonsillopharyngitis. The spectrum of its pharmacological properties includes antiviral, anti-inflammatory, and immunomodulatory action. The aggregate of these properties allows affecting almost all pathogenetic process links underlying the nosology in question, and favourable safety profile allows viewing Imupret as a basic therapeutic agent in treatment of non-bacterial forms of acute tonsillitis, pharyngitis, and tonsillopharyngitis. Our previous work showed that the use of Imupret in patients with non-bacterial tonsillitis accelerates regression of symptoms of tonsillitis and reduces the need for antibiotics. At the same time, there is a lack of studies, valid from the viewpoint of compliance with GCP standards have been conducted. Confirmation of high efficacy of Imupret in treatment of the above nosology group would be served as a justification for optimization of this nosology treatment scheme of delayed antibiotic prescription and recommendations for inclusion of this drug product into the national guidelines.

In the context of this clinical trial the two questions that are to be answered are:

1. Does Imupret®, taken during the diseases acute period help reduce the frequency of antibiotic use in children aged 6-12 ?
2. Does Imupret®, taken during the diseases acute period helps to accelerate the regression of symptoms in children aged 6-12?
3. Is the use of antibiotic delay technology safe for children aged 6-12 years?

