8.3.3 Reference treatment

All patients of the trial will undergo the reference treatment described below. However, only one of the two study groups (study group 1) will receive and add-on treatment with either Imupret® oral solution (see 0 and 8.3.2).

Reference treatment comprises instructions for patient's behavior as well as possible medical treatment when needed:

- Sparing diet with fractional feeding (5-6 times a day) in only small portions explicitly excluding coarse, spicy, or heavily digestible food
- At the discretion of the investigator, elimination of all factors irritating pharyngeal mucosa (e.g. thermal, chemical influence etc.)

At the discretion of the investigator, Paracetamol as single doses up to 500 mg – not more than 3-4 times daily

- At the discretion of the investigator, topical treatment like benzydamine, lidocaine (in case of severe sore throat)
- At the discretion of the investigator, antibiotic treatment in case it is indicated with e.g. amoxicillin clavulanate, cephalosporins (in case of prescription of antibiotics patients will be evaluated separately)

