8.4 Randomization

The clinical part of the trial will be open and randomized with no blinding procedure. Subjects will be randomly assigned to one of the two possible treatments with according to the underlying randomization list. Randomization will be performed using [StatSoft – generator of random figures] software.

The appropriate number of the randomisation schedule and associated treatment will be allocated for each subject whose entry in the randomised part of the clinical trial is confirmed. The randomisation list will be part of the trial documentation.

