12.2.2 Primary endpoint

Main criterion for evaluation in the trial will be:

- Scores determined by the Local Tonsillitis Manifestations Scale refined by McIsaac's scale. Scores will be dichotomized to decide for two categories (therapy effective/therapy ineffective).
Scores will be evaluated by treatment and time point, i.e. per visit
- Need for an antibacterial therapy, i.e. number of patients per treatment.

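### Antibiotic need can by itself decide failure on the main criterion, yet an unblinded investigator judges it with no operational criterion

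*Protocol*

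**What the plan says.** **Role in the main criterion.** The synopsis (Efficacy endpoints) requires two things for a success: each local symptom down to 1 point or less, and "Absence of indications for prescribing antibacterial therapy". Anything short of that is a failure. Protocol 12.2.2 and the SAP (Primary endpoint) add a second main item: "Need for an antibacterial therapy, i.e. number of patients per treatment". Antibiotic need is also the first objective in Protocol 7 and the first question in 6.3.

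**Who decides.** Protocol 10.2, Visit 2: "The investigator will estimate indicators for prescription of antibiotics and will decide whether a patient will remain on the study treatment or not". Protocol 8.3.3, for all patients: "At the discretion of the investigator, antibiotic treatment in case it is indicated".

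**Blinding.** Protocol 8.4: "The clinical part of the trial will be open and randomized with no blinding procedure". No independent or blinded assessor is described.

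**Nearest things to a criterion.**
- Protocol 6.1 (background): "In the absence of positive effect within 36-48 hours from the beginning of treatment with Imupret the antibacterial therapy with antibiotics is started".
- Protocol 6.1 also names the McIsaac scale as a tool for identifying who should receive an antibiotic.
- Protocol 8.5 mentions an axillary temperature above 38.0 °C from day 3 on, as a reason for an unscheduled visit.

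**Antibiotic users.** Protocol 8.3.3 and 10.2 say that they are evaluated separately. Neither section says that they also stay in the main comparison.

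**The concern.** In an open trial, an outcome that consists of a treatment decision is only as comparable between arms as the rule behind it. Here the decision-maker knows the arm and has no written threshold. Two children with the same temperature, nodes and throat findings at Visit 2 can get different decisions, and one such decision turns a success into a failure. Both main criteria would move together, because both depend on the same judgement.

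The separate evaluation of antibiotic users adds a second exposure. Under the synopsis definition these children are failures. If they were analysed apart, the remaining comparison would be conditioned on an outcome that arises after randomisation and is decided with knowledge of the arm.

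Neither problem can be repaired at analysis: a threshold that was never set, and a reason that was never recorded, cannot be recovered from the database.

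**Working it through.** **1. Is there an operational criterion?** Each candidate in turn:

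| Candidate | Where | Why it does not settle the decision |
|---|---|---|
| No positive effect by 36-48 hours | Protocol 6.1 | Positive effect is undefined; the sentence speaks of Imupret treatment only |
| McIsaac score | Protocol 6.1, 9.2, 10.2 | All children enter at 4-5, where 6.1 sees no unconditional indication; it is re-scored at Visit 2, but no cut-off is given |
| Temperature above 38.0 °C | Protocol 8.5 | Triggers an unscheduled visit, not an antibiotic |
| SAP | Primary endpoint | Adds no criterion |

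The McIsaac score could separate children at Visit 2, since fever, painful nodes and tonsillar findings can resolve. What is missing is the cut-off.

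**2. The plan's own figure.** With 75% and 90% success, z-values 1.96 and 0.84, and a difference of 0.15 (synopsis, Table 1):

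n = (1.96 + 0.84)² × [0.75 × 0.25 + 0.90 × 0.10] / 0.15² = 7.84 × 0.2775 / 0.0225 = 96.7, rounded up to 97 per group, and 97 + 3 = 100 with dropout.

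This reproduces the plan and is not disputed. It supplies the rates and group size used below.

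**3. Sensitivity of the composite (illustration).** The documents give no antibiotic rate, no size for arm-dependent prescribing and no fixed test. Assumed: 100 per arm, two-sided 5% pooled chi-square test, exact enumeration over two binomials. Each net extra indication among would-be successes moves that arm's success rate by 1/100 = 1 percentage point. The plan's clinically important difference is 15 points.

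No true effect, 75% success in both arms:

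| Net extra indications per 100 in one arm | Chance of a significant result for the other arm, all on would-be successes | Same, half on children who fail on symptoms anyway |
|---|---|---|
| 0 | 2.5% | 2.5% |
| 5 | 12.1% (75% vs 70%) | 5.9% (75% vs 72.5%) |
| 10 | 34.2% (75% vs 65%) | 12.1% (75% vs 70%) |
| 15 | 62.6% (75% vs 60%) | 21.6% (75% vs 67.5%) |

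The table is the same with the arms swapped.

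With the plan's rates as the true ones (90% Imupret, 75% reference), power is 81.6%. It becomes 95.6% with a net 5 extra in the reference arm (90% vs 70%) and 43.0% with a net 5 extra in the Imupret arm (85% vs 75%).

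**4. How many decisions matter.** From a tie at 75/100, take 13 successes from one arm: 75 vs 62, pooled rate 137/200 = 0.685, standard error √(0.685 × 0.315 × 2/100) = 0.0657, z = 0.13/0.0657 = 1.98, p = 0.048. With 12 (75 vs 63), p = 0.067.

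**5. Which composite should lead.** Suppose no true effect, 75% success, and 10 net off-criterion starts in the reference arm, half on would-be successes.
- Any antibiotic counted as failure: 75% Imupret vs 70% reference. Chance of a false significant result for Imupret: about 12%.
- Only criterion-based indications counted: from 75% vs 75% (antibiotic does not change symptoms) to 75% vs 80% (all five would-be failures cured). At that upper end, the chance of a false significant result for the reference arm is about 13%.

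The two versions can err in opposite directions, so both are needed. The first answers the question in Protocol 6.3 about how often antibiotics are used; the second can credit an antibiotic-treated child as a success.

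**The case against.** **Judgement is inherent in delayed prescribing.** This is a phase IV open trial in children, and rigid rules could be unsafe. That stands, and the fix therefore keeps the investigator free to prescribe.

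**A rule is stated.** Protocol 6.1 gives a time window and names the McIsaac scale. It would be wrong to say that there is no criterion at all; what is absent is one that could be applied in the same way by two people.

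**Visit 2 findings are recorded in both arms.** Protocol 10.2 describes the examination and scores ahead of the decision and requires details of any prescription. Antibiotic starts can thus be compared between arms given the recorded findings. The check is partial: no reason is tied to a fixed criterion, and the scores come from the same unblinded setting.

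**The trial is called exploratory** (Protocol 8.2, 12.2). But the synopsis plans a superiority comparison with 80% power, and Protocol 6.1 and 6.3 look to the result to support inclusion in national guidelines.

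**Direction.** A reader might infer that the bias must favour Imupret, because Protocol 6.3 says of earlier work that "the use of Imupret in patients with non-bacterial tonsillitis accelerates regression of symptoms of tonsillitis and reduces the need for antibiotics". That sentence concerns non-bacterial tonsillitis, whereas this trial enrols children at McIsaac 4-5, for whom the protocol gives a streptococcal probability of about 50%. On parental pressure, Protocol 6.1 says that "one should distinguish the desire of the patient or his parents to get rid of the pain, from the rational assessment of the doctor", which is guidance against yielding to it. A shift towards Imupret is plausible, but the documents do not establish it.

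**Conclusion.** The point holds in limited form. An antibiotic indication is enough for failure under the synopsis definition and is a main criterion again in Protocol 12.2.2 and the SAP. It is decided at the discretion of an investigator who knows the arm, without an operational criterion. Arm-dependent judgement could move both main criteria either way.

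Three stronger readings are not supported:
- **An unequal threshold for the two arms.** The 36-48 hour sentence mentions only Imupret, but it is background text; Protocol 8.3.3 and 10.2 are worded for both arms.
- **Exclusion of antibiotic users from the main analysis.** The text says only that they are evaluated separately. Exclusion is one way to carry that out, and it would contradict the synopsis.
- **A bias of known size.** The shifts of 5 to 15 per 100 are assumed. They show how sensitive the composite is and carry no weight in judging how serious the gap is.

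The recommendation rests on the missing threshold, the unclear place of antibiotic users, and the low cost of settling both before enrolment. It should be done.

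**What to change.** **Protocol, before enrolment.**
- Have the sponsor's clinicians set antibiotic-indication criteria, worded identically for both arms, for Visit 2, for Visit 3 if it becomes a visit, and for unscheduled visits.
- Base them on data already collected: temperature, the local scale and the McIsaac components (synopsis, Methodology; Protocol 10.2). Say which local-scale items count, since Protocol 8.5 lists five and 10.6 lists seven.
- Require the scores to be completed before the decision.
- Add one CRF field: the criterion met, or other/parent request. Investigators remain free to prescribe outside the criteria.

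**SAP.**
- Keep antibiotic users in the main comparison within the stated analysis set; any separate evaluation is an addition.
- In the main version, count any antibiotic start or indication as failure, in line with the first question in Protocol 6.3.
- Report by arm, as sensitivity analyses: the criterion-based composite; starts on and off the criteria; and the symptom-only responder rate, noting that an antibiotic can itself improve Visit 4 symptoms.

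**Cost.** A short list of criteria, one CRF field, three tables and a few sentences in the SAP. No added visits, staff or procedures; slightly more documentation.

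**What remains.** Symptom scoring is still unblinded, including where the criteria use the local scale, and the main version still counts discretionary starts. The fix gives both arms a common threshold and makes departures from it visible; it does not remove the bias.

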12.2 Statistical evaluation

The statistical planning of the trial and the statistical analyses will be conducted following the principles specified in the ICH Topic E9 (ICH, 1998), and will be carried out by a qualified statistician in accordance with the ICH. Technical details of the statistical analyses will be specified prior to data analyses.

In general, there will be one main statistical evaluation.

Data base will be closed after all data are entered and cleaned.

In general, unless otherwise stated, continuous data will be summarized by means of descriptive statistics (mean, standard deviation (SD), median, quartiles, minimum, and maximum). Categorical variables will be described in contingency tables as absolute number and percentages.

AEs will be evaluated considering frequency and intensity. Furthermore, AEs will be evaluated considering relationship to the IMP, outcome, and seriousness. Both will be described by absolute and relative frequency. Descriptive statistics will be calculated for clinical laboratory parameters determined. Frequencies of values inside and out of normal range (i.e. above and below) will be given where possible.

This is an exploratory trial with no formal sample size estimation. Therefore, beneath descriptive statistics of efficacy endpoints, concluding statistics may be performed in a data driven way, in order to find clinically relevant differences between study participants, time points and treatments. Possible corrections to prevent an alpha inflation will be performed, if meaningful.

Specifications of the biometrical evaluation will be defined after all data management processes of the study phase will be terminated and data base was closed. In general, variables will be analyzed considering the underlying analysis set, treatment and time point, if meaningful.

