12.2.1 Analysis sets

Full Analysis Set (FAS)

The FAS consists of all randomized patients with at least one documented application of IMP and with at least one observed post-baseline value.

Per Protocol Set (PPS)

The PPS consists of all patients of the FAS without major protocol deviations. The evaluation of protocol deviations and whether they lead to the exclusion of a patient from the PPS will be performed during data review of the study.

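### The plan says antibiotic users are evaluated separately but never says how they enter the main comparison, where the synopsis would score them as failures

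*Protocol*

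**What the plan says.** Two protocol sections set antibiotic patients apart. Section 8.3.3 (Reference treatment) does so on prescription: "in case of prescription of antibiotics patients will be evaluated separately". Section 10.2 (Visit 2) does so on intake: "Patients with intake of antibiotics will be evaluated separately". Neither says what separate evaluation means.

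The synopsis (section 5, Efficacy endpoints) uses a third trigger, the indication. To count as effective, a patient needs low symptom scores and also "Absence of indications for prescribing antibacterial therapy". The other category is residual: "Treatment is not effective - the condition given for the category" of effective therapy is not met. A patient with an antibiotic indication is therefore a failure inside the main variable.

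Section 12.2.2 and the SAP's Primary endpoint section take over neither rule. They list a dichotomised symptom score with no stated antibiotic component and, as its own bullet, "Need for an antibacterial therapy, i.e. number of patients per treatment".

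The full analysis set (section 12.2.1 and the SAP) has no exclusion for antibiotic use: "The FAS consists of all randomized patients with at least one documented application of IMP and with at least one observed post-baseline value". The per-protocol set removes major protocol deviations, without saying whether antibiotic use is one.

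On timing, section 12.2 and the SAP state: "Specifications of the biometrical evaluation will be defined after all data management processes of the study phase will be terminated" and the database closed. On blinding, section 8.4 states: "The clinical part of the trial will be open and randomized with no blinding procedure".

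**The concern.** Starting an antibiotic is the failure event of the delayed-prescription strategy (section 6.1). Reducing antibiotic use is the first trial question (section 6.3) and the first objective (section 7). The decision is taken at Visit 2 by an investigator who knows the arm. It is therefore an outcome of randomised treatment, open to influence by knowledge of that treatment.

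If separate evaluation means an extra table of antibiotic users, nothing is lost. If it means removing them from the effective/ineffective, symptom, temperature and VAS comparisons, those comparisons are made between groups selected on a post-randomisation outcome, and the bias can go in either direction. Removal could come through the per-protocol set, by calling antibiotic use a major deviation, or through an analysis outside the two named sets. The plan does not say which meaning applies.

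**Working it through.** **Inputs.** From the synopsis sample size table: control success 0.75, Imupret success 0.90, two-sided 0.05 (z = 1.96), 80% power (z = 0.84), 97 per arm raised to 100. The documents give no antibiotic rate, so it is varied below as an assumption.

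**The plan's own figure.** (1.96 + 0.84)² × (0.75 × 0.25 + 0.90 × 0.10) / 0.15² = 7.84 × 0.2775 / 0.0225 = 96.7, so 97 per arm. It reproduces as a test of a 15-point difference against zero, and that test is used below.

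**Case A: synopsis composite, everyone left out is a failure.** Let s be the share of an arm's failures left out and p its true success rate. Of n patients, n(1 − p)s are left out, n[1 − (1 − p)s] remain, and the success rate among them is p / [1 − (1 − p)s]. Power uses an unpooled Wald test. With n = 100 and the same s in both arms:

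| s | Left out, control / Imupret | Success, control / Imupret | Difference (points) | Power |
|---|---|---|---|---|
| 0 | 0 / 0 | 75.0% / 90.0% | 15.0 | 81% |
| 25% | 6.25 / 2.5 | 80.0% / 92.3% | 12.3 | 70% |
| 50% | 12.5 / 5 | 85.7% / 94.7% | 9.0 | 54% |
| 75% | 18.75 / 7.5 | 92.3% / 97.3% | 5.0 | 31% |
| 100% | 25 / 10 | 100% / 100% | 0 | none |

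For the 50% row: 0.90/0.95 − 0.75/0.875 = 0.947 − 0.857 = 0.090. The standard error is √(0.857 × 0.143/87.5 + 0.947 × 0.053/95) = 0.0439, and 0.0902/0.0439 − 1.96 = 0.10, which gives 54%. With 97 per arm the five power figures are 80%, 69%, 53%, 30% and none.

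**Case B: score-only variable, as section 12.2.2 and the SAP list it.** An antibiotic user may have recovered by day 10 and count as a responder. Assume 90% versus 75% on the score alone and that half of those left out are responders. Leaving out 5 Imupret and 12.5 control patients gives (90 − 2.5)/95 = 92.1% and (75 − 6.25)/87.5 = 78.6%. The difference is 13.5 points with 74% power, compared with 9.0 points and 54% in case A.

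**Case C: no true effect, 75% in both arms, unequal shares left out.**

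- Modest, composite: 50% of failures left out in one arm and 40% in the other gives 0.75/0.875 − 0.75/0.90 = 0.857 − 0.833, or 2.4 points. About 7% of trials would be significant.
- Extreme, composite: 75% versus 25% gives 0.75/0.8125 − 0.75/0.9375 = 0.923 − 0.800, or 12.3 points, with about 68% significant.
- The same extreme numbers (18.75 versus 6.25 left out) on the score-only variable, half of them responders: 65.625/81.25 − 71.875/93.75 = 0.808 − 0.767, or 4.1 points, with about 10% significant.

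The shift favours the arm that loses more failures. A false advantage for Imupret therefore needs more antibiotic users on Imupret, and the antibiotic count per arm would show that. Fewer users on Imupret, the direction the trial hopes for, moves the result against Imupret.

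**Kept in as failures.** The result is 15.0 points and 81% power, or 0 points and 5% significant with no true effect.

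**The case against.** The strongest reply is that the plan contains an undefined word and not two conflicting rules. No section says antibiotic users are left out. The synopsis scores them, section 12.2.2 counts them by arm, and the full analysis set does not exclude them. A separate display fits all of this. That stands, and it makes the harm conditional.

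Second, timing is partly controlled. Section 12.1 locks the database only after the analysis sets are documented, and section 12.2 and the SAP promise technical details before the analyses. That narrows the risk without removing it. The same section and the SAP defer the specifications until after closure, treatment is known throughout an open-label trial, and separate handling could be done outside the named sets.

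Third, the larger figures depend on the model. Case A needs every excluded patient to be a failure, and the 68% needs a threefold imbalance in the share excluded. Both limits are accepted. The trial also describes itself as exploratory, names no test in section 12.2 or the SAP, and its synopsis states a 15-point superiority margin that the test against zero does not use.

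A reader might infer that the plan excludes antibiotic users, or that it would produce false positives about two times in three. The documents support neither: exclusion is only one reading of an undefined word, and the two-in-three figure belongs to one extreme case under that reading.

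**Conclusion.** The concern holds as an unresolved ambiguity in the main comparison. The documents lean towards the harmless reading, under which antibiotic users stay in as failures and no bias arises. They do not rule out exclusion, which would condition the comparison on an unblinded outcome of treatment.

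Under exclusion, the size depends on an antibiotic rate the documents do not give. At the planned success rates, the loss runs from 15.0 to between 12.3 and 5.0 points when 25% to 75% of failures are removed equally. It is 1.5 points (15.0 to 13.5) in the score-only illustration. With no true effect, the shift runs from about 2 points to 12.3 points in the extreme case, in either direction. These are illustrations of sensitivity, not predictions. The antibiotic count per arm is the same on every reading.

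This should be fixed. It does not by itself invalidate the design.

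**What to change.** Before database closure, replace the two sentences on separate evaluation in protocol sections 8.3.3 and 10.2, and add to section 12.2 and the SAP wording such as:

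> Patients who meet the antibiotic criterion remain in their randomised arm and are scored not effective in the main variable, as in the synopsis. They are not removed from any full-analysis-set comparison because of antibiotic use. Antibiotic use alone is not a major protocol deviation for the per-protocol set. Separate tables of antibiotic users are supplementary.

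Three further alignments are needed:

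- Bring the dichotomised variable in section 12.2.2 and the SAP into line with the synopsis composite.
- Reconcile indication (synopsis), prescription (8.3.3) and intake (10.2) to one trigger recorded in the CRF, as an endpoint definition only and not a treatment rule. Section 6.1 describes the delayed prescription as written in advance, so prescription alone needs a precise meaning.
- State the visit from which the failure score applies.

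The cost is wording in two documents. Section 10.2 already has prescription details and intake documented; one CRF field may be needed if the trigger is indication.

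There are downsides. Symptom, temperature and VAS values after an antibiotic include its effect, which the supplementary tables can show. Open-label prescribing still influences the antibiotic component. Sections 8.3.4 and 9.4.1 allow discretionary withdrawal, so some users may lack later values, and the documents give no rule for those gaps.
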